Moreover, new technologies developed by our center in collaboration with external partners (Neuroelectrics, Barcelona, Spain) might help to further increase the precision of tACS targeting, allowing for individualized stimulation solutions based on modeling of current distribution using structural MRI scans. The first generation of devices for transcranial electrical stimulation only allowed for stimulation protocols including two electrodes, limiting the number of target regions to no more than two. Moreover, this solution did not allow for careful mapping of individual brain anatomy, and therefore resulted in sub-optimal stimulation patterns. Current approaches for so-called multi-focal stimulation (Ruffini, Fox, Ripolles, Miranda, & Pascual-Leone, 2014) permit stimulation montages based on up to 32 stimulating channels, with the precise stimulation pattern defined by means of modeling of induced electric field based on individual T1-weighted MRI scans. This results in more accurate, individualized montages, which might become crucial when targeting amyloid in AD patients.

Also, genetic testing is increasingly playing a role in the understanding of the etiology of AD. In particular, certain polymorphisms in the gene which codes for the apolipoprotein E (ApoE) have been linked to increased risk of developing AD, specifically with carriers of the $\epsilon 4$ allele (Risacher et al., 2013). Furthermore, there is at least some evidence that ApoE- $\epsilon 4$ may impact response to non-invasive brain

stimulation (Peña-Gomez et al., 2012), therefore potentially modulating the effect of tACS.

This study will leverage all this accumulated knowledge by implementing an intervention based on multiple, individualized multifocal tACS stimulation sessions based on individual PET and MRI information in patients with amyloid-positive PET.

B3. DESCRIPTION OF RESEARCH PROTOCOL

A. Study Design – Overview, Methods, Procedures

Overview

This is a safety and feasibility study of tACS in patients diagnosed with early AD. Individuals who have had amyloid PET imaging and have evidence of cerebral amyloid burden will be recruited. Individuals with a diagnosis of mild Alzheimer's Disease and suspected amyloid burden will also be recruited and undergo a PET scan during the screening process. All subjects will receive 10 sessions of active tACS targeted on a case-by-case basis to the regions of tracer uptake on the amyloid PET study.

Study Design

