The study will be conducted at BIDMC, at the Berenson-Allen Center for Noninvasive Brain Stimulation and in the Clinical Research Center. We aim to study 10 individuals with AD with evidence of increased cerebral amyloid burden on amyloid PET imaging. Up to 20 participants will be enrolled to account for attrition. Each subject's participation in the study will consist of up to 18 visits: 4-5 days for screening/baseline procedures as described below (these baseline assessments may happen over 4-5 days to accommodate scheduling and the participant), 10 tACS study visits, and 4-5 days for follow-up assessments. Subjects will undergo baseline cognitive assessment, structural and functional MRI characterization, resting-state EEG measurement and amyloid PET scan (if not previously obtained). Additionally, patients will undergo a TMS-EEG and a tACS-EEG recording session to assess brain plasticity levels and identify markers of response to stimulation. All subjects will subsequently undergo 10 sessions of gamma-frequency (40 Hz) tACS. The stimulation sites will be identified on a case-by-case basis taking into account the overall distribution of amyloid- β as evidenced by the amyloid PET scan. Subjects will take a standardized adverse effect questionnaire before and after each session to demonstrate safety and tolerability (Fertonani et al., 2015). At the end of the 10 sessions, subjects will then repeat the baseline assessments, followed by repeat amyloid PET imaging to assess for changes in amyloid burden.

Procedures

Screening and Baseline Visit (Visits 1-4)

During the screening and baseline visit, participants will provide informed consent and complete the following procedures:

- Neurological exam*
- Demographic review*
- Review of medical, psychiatric and medication history, including review of diagnosis*
- tACS and TMS safety questionnaires*
- MMSE*
- The Clinical Dementia Rating (CDR) scale to assess severity of dementia*
- Inclusion/Exclusion criteria review*
- MRI screening questionnaire
- Alzheimer's Disease Assessment Scale Cognitive Subscale (ADAS-Cog)
- Baseline Clinical Global Impression of Change (CGIC)

- National Alzheimer's Coordinating Center's Uniform Data Set (NACC-UDS) questionnaires: Activities of Daily Living Inventory (ADL); Geriatric Depression Scale (GDS); Functional Assessment Questionnaire (FAQ)

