- National Alzheimer's Coordinating Center's Uniform Data Set (NACC-UDS) battery that includes the MoCA, Number Span Forward & Backward, Trail Making Test, Figure Copy, Story Recall, Digit Symbol, and Multilingual Naming Test, Verbal Fluency, Category Fluency. Only portions of this set may be completed, although the number span will be done in all cases. The MoCA will serve as the baseline cognitive assessment for monitoring cognition throughout the study.
- Brief estimate of intelligence using the Wechsler Test of Adult Reading (WTAR)
- Rey Auditory Verbal Learning test (RAVLT) as measure of learning and memory
- Modified Edinburgh Questionnaire to determine handedness
- Pregnancy test for females of child-bearing potential
- Saliva for DNA and tau (this may be collected at any visit)
 - Three saliva samples will be taken:
 - One sample for tau protein
 - Two optional samples for BDNF and APOE genotyping (this may be collected at visit #2 if the subject has trouble producing additional saliva following the first collection)
- fMRI - Patients who have had an fMRI in another study in the Berenson-Allen Center within 6 months (pending the quality of the images) may not have to repeat this scan
- PET Imaging
- Lumbar puncture** (optional)
- Blood draw**
- TMS-EEG plasticity assessment
- tACS-EEG recording with cognitive tasks

The screening and baseline visits will occur over 4-5 days. All of the screening activities necessary for determining inclusion and safety will be completed on the first day as indicated by the asterisks above (*). The remainder of the activities will be planned according to scheduling, resources, timing and subject tolerability. It is possible that there would be an additional visit due to these issues. It is possible that a baseline activity will happen on the first day of stimulation prior to the tACS (e.g. a questionnaire).

**If the participant agrees to an LP, blood and CSF will be sent for real-time analysis (e.g. Labcorp) of CBC, glucose, and protein to assess for any incidental LP finding such as indicators that there is concern for an inflammatory process. CSF and blood will also be processed and stored for analysis of AD biomarkers at the end of the study. If the participant does not agree to the LP, the blood will only be analyzed for AD biomarkers at the end of the study.

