- Cognitive Evaluation that includes the MMSE, NACC-UDS questionnaires and cognitive assessments completed at baseline, RAVLT, ADAS-Cog, and CGIC.
- Repeat baseline UDS questionnaires
- PET Imaging – A follow-up PET scan will be obtained to assess the change in amyloid burden in the stimulated target region
- fMRI
- Lumbar puncture (optional)
- Blood draw
- TMS-EEG plasticity assessment
- tACS-EEG with cognitive tasks
- Adverse event review and follow-up
- Review of medications and changes in medical history
- At the completion of the study, subjects will be queried about their overall experience with the study using the Participant Experience Assessment

It is possible that the follow-up visit will be conducted over 4-5 days due to availability of the PET scanner and resource availability.

If participants have plasticity measures or neuropsychological testing from a prior study in the B-A Center, those may be compared to the measures obtained in this study and/or used in place of the testing in this study.

Telephone Follow-up After (1 month and 3 months after completion of visit 18)

The following will occur via telephone call at two time points, approximately 1 month and 3 months after the participant completes the in-person follow-up visits. for assessment of any longer term changes:

Measures that were collected during prior visits will be completed via telephone:

- Telephone version of MoCA completed with study participant
- CGIC to be completed with study participant and study partner
- Activities of Daily Living Inventory (ADL) –(the number of questions in this may be reduced)

For study participants who already completed the study we plan to complete the telephone follow-up retroactively. If the participant has already passed the 1 month follow-up mark, but not the 3 month mark we plan to call them at two time marks-- immediately and at the 3 month mark. If the participant has already passed both the 1 month and 3 month marks, we plan to complete the follow-up assessment with them at one time mark, following up with them as soon as possible.

Methods

Cognitive Measures

Alzheimer's Disease Assessment Scale (ADAS-Cog):

The ADAS-Cog is a standardized neuropsychological assessment that measures the severity of symptoms of Alzheimer's Disease in 11 different domains. The tasks assess the domains of language, praxis, memory, attention and executive function.

Alzheimer's Disease Cooperative Group Study Clinical Global Impression of Change (CGIC):

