can slide into the scanner. Subjects will be handed the emergency button which they can squeeze at any point during the procedure to inform the investigators if they have a question, are feeling uncomfortable, or are in distress. The subject's head will be carefully positioned and foam-padded cushions will be placed on either side of their head in order to prevent movement during the scanning session. The subject will receive earplugs to wear during the entire scanning session in order to minimize the noise of the scanning machine. The subject will then undergo a series of MRI scans of the brain. Structural images will be acquired followed by resting-state functional MRI scans. Total scan time will be about 50 min.

The MRI done in this study is for research purposes only. It will not be read by a radiologist. If there are incidental findings noted on the MRI, the subject will be notified and advised to see their primary care provider for a diagnostic MRI.

For safety reasons, participants whose abdomen, shoulder, or hip circumference is greater than 180cm may need to be excluded from the study.

PET

An amyloid PET scan will be conducted at baseline. A follow-up PET scan will be obtained after the completion of the tACS sessions. PET imaging with Florbetapir-[18]F injection will be performed on BIDMC's Siemens Biograph m64 multidimensional helical PET-CT Scanner. A 10 minute emission scan, acquired with a 128 x 128 matrix (zoom 2) in 1 x 10min frames, will be obtained 30-50 minutes after intravenous injection of 10 mCi (370 Mbq) of Florbetapir F18 (or Florbetaben).

The follow-up PET imaging to be done in this study is the equivalent of a clinical PET study using a ligand that is FDA approved for assessing A β burden. This ligand is the same as the ligand used in the PET obtained prior to enrollment. The scan will be read by a nuclear medicine physician and a report will be prepared.

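### Tests from earlier studies, and earlier amyloid scans, may stand in for this study's own measurements with no limit on their age

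*Combined protocol and SAP*

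**What the plan says.** **Cognition and plasticity.** The Follow Up Visit section (B3.A) ends by saying that plasticity or neuropsychological measures from an earlier study at the center may be compared with this study's measures, or "those may be compared to the measures obtained in this study and/or used in place of the testing in this study". No maximum age is given, and the sentence does not say that only baseline tests may be replaced. By contrast, the baseline procedure list limits reuse of fMRI to "Patients who have had an fMRI in another study in the Berenson-Allen Center within 6 months", subject to image quality.

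**Amyloid PET.** Study Design lists a baseline "resting-state EEG measurement and amyloid PET scan (if not previously obtained"). The Overview fits that rule: it describes a screening scan only for patients whose "suspected amyloid burden will also be recruited and undergo a PET scan during the screening process". The PET methods section says "An amyloid PET scan will be conducted at baseline", yet also refers to a scan obtained before enrollment. It names one scanner, the "Siemens Biograph m64 multidimensional helical PET-CT Scanner", and states that the follow-up ligand matches the pre-enrollment one, but it allows 10 mCi "of Florbetapir F18 (or Florbetaben"). The same section and B6 Recruitment allow earlier scans, including scans from outside hospitals, to be obtained and used or compared, without an age limit. The PET risk text in B5 counts three scans.

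**Analysis.** B3.B tests changes in amyloid, EEG, cognition and plasticity by paired t test at 0.05. It judges individual amyloid change against a figure of 0.05 SUVR per year, and counts either a decrease or a slower build-up as an effect.

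**The concern.** There is no control arm, so the only protection against natural change is a short, uniform interval between the two measurements. B3.B uses that argument explicitly for amyloid. A baseline of unknown age removes it: the pre-post difference then contains disease course since the earlier study or scan as well as any tACS effect.

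The reuse sentence for cognitive and plasticity tests is the more serious part, because it is an express permission to substitute data in outcomes of Aim 3 and Exploratory Aim 2. Read literally, it would even let a test taken before tACS stand for the post-treatment test, which would leave nothing to compare. For amyloid (Aim 2) the wording leaves open which scan is the paired baseline, and a threshold quoted per year has no fixed meaning when intervals differ between patients.

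**Working it through.** **1. Who has an in-study baseline scan?**

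| Place | Reading |
|---|---|
| Overview; Study Design | In-study scan only if none exists |
| Baseline procedure list | PET listed with no waiver |
| PET methods | Baseline scan for all, but also a pre-enrollment scan |
| PET methods (earlier scans); B6 Recruitment | Earlier scans may be used; role not settled |
| B5 risk text | Three scans, 24 mSv, so 24/3 = 8 mSv each |
| Study Visit Schedule | Two scans, no waiver shown |

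Two scheduled scans, or one after a waiver, do not match three. The schedule row is weak evidence of a scan for all: the fMRI row carries no waiver either, although fMRI is expressly waivable.

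**2. Amyloid drift.** B3.B describes change as between nothing (the plateau) and about +0.05 SUVR per year. Drift = (0 to 0.05) × age of baseline in years.

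- 3 to 6 weeks (assumed in-study interval: 4-5 screening days, 10 weekday sessions, follow-up within about a week): upper values 0.05 × 3/52 = 0.003 and 0.05 × 6/52 = 0.006
- 6 months: 0 to 0.025
- 1 year: 0 to 0.05

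**3. Individual decrease.** Assumptions: SUVR 1.6 (the positivity cut-off), true fall 0.10, and the plan's 3% error read as the SD of the change (0.03 × 1.6 = 0.048) or as a per-scan SD (0.048 × √2 = 0.068). P(measured fall > 0.05) = Φ((0.05 − drift)/SD):

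- no drift: 77-85%
- 6 months, upper-case drift: 64-70%
- 1 year, upper-case drift: 50%

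**4. Group mean, six completers** (the plan expects 5/6). With k one-year-old scans at upper-case drift, the mean shifts by k × 0.05/6: 0.008, 0.017 and 0.025 for k = 1, 2 and 3. The standard error is 0.048/√6 = 0.020 to 0.068/√6 = 0.028.

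**5. Keep or drop older pairs?** Power of the two-sided 0.05 paired t test, true mean fall 0.10, SD 0.048 / 0.068 (simulation for keeping, noncentral t for dropping):

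| One-year-old scans | Keep all six | Drop those pairs |
|---|---|---|
| 0 | 98% / 82% | – |
| 1 | 94% / 72% | 93% / 70% |
| 2 | 86% / 62% | 78% / 52% |
| 3 | 78% / 53% | 50% / 31% |

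Even at upper-case drift, dropping costs as much power as keeping, or more. At zero drift, keeping costs nothing. At SUVR 2.0 (SD 0.060 / 0.085), power with no old scans is already lower, at 90% / 64%.

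**6. Slower build-up.** Take a patient on the plateau with a one-year-old scan and no tACS effect. Observed change is 0. Against the typical +0.05 per year, that is a shortfall of 0.05 × 1 = 0.05, as large as the plan's own figure. Over six weeks the same comparison gives 0.006, far below the measurement error. A long interval therefore makes this half of the response definition easier to meet by natural history alone.

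**7. Cognition and plasticity.** The documents give neither a rate of change nor an SD for these measures, so no size can be calculated.

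**The case against.** The PET wording can largely be read as one rule, that a prior positive scan may serve, with a general sentence in the methods section and a bare list entry left over. That is fair, and a reader who infers from the visit schedule that every patient must be rescanned goes further than the documents allow. Earlier scans may be meant only for eligibility, targeting or trajectory.

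A reader might also infer that old scans could produce a false amyloid reduction. The plan's own drift is upward or zero, so it works against finding a fall. It may well be zero here, since B3.B places the plateau in patients with cognitive deficits and high amyloid. The larger losses above use the upper case, an assumed fall of 0.10 and an SUVR at the cut-off.

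The test substitution is permissive and may never be used. Parts of the battery look protected: the baseline MMSE is fixed to screening day 1, and "The MoCA will serve as the baseline cognitive assessment for monitoring cognition throughout the study". Resting-state EEG is scheduled separately, although the TMS-EEG session also contains a resting recording, and the plan does not say whether that counts as a plasticity measure.

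What stands: substitution without a time limit or a restriction to baseline, an undated PET waiver, unreconciled scan counts, and a per-year criterion applied to unequal intervals.

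**Conclusion.** The concern holds, chiefly for the replaceable Aim 3 cognitive tests and the exploratory plasticity measures. There, a stated rule would give a confounded pre-post change if followed. Its size is unknown, as is the number of patients affected.

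For Aim 2 the effect is smaller: 0 to 0.05 SUVR per patient with a one-year-old scan, and at most 0.008 per such patient in a mean of six, in the direction that hides a fall. The exception is the slower-build-up criterion, where a long interval can favor a positive reading. These figures rest on the plan's 0 to 0.05 per year and on the SD, SUVR and effect assumptions stated above. Scans older than a year, or a change of tracer or scanner, are not quantified.

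The documents do not support concluding that the amyloid test as a whole is invalid, or that older pairs must be excluded. Safety (Aim 1) is unaffected.

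**What to change.** (a) In the Follow Up Visit section, remove the permission to replace this study's testing for any pre-post outcome. Alternatively, limit it to baseline and to a stated short window, for example no longer than the six months used for fMRI. That figure is only a precedent within the protocol; nothing ties it to cognitive change. Never allow substitution for post-treatment tests. Cost: some patients repeat tests that are already scheduled.

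(b) Reconcile the Overview, Study Design, baseline procedure list, PET methods, B5 risk text and B6 Recruitment on who has an in-study baseline scan, how many scans there are, and what earlier scans are for. Use the in-study scan as the paired baseline wherever one is obtained. If earlier scans do serve as baseline, keep those pairs in the main analysis, list scan age, tracer and scanner per patient, and add a sensitivity analysis limited to recent scans with the same tracer and scanner. Cost: wording, one listing and one low-powered extra analysis (with four pairs, 78% / 52% under the assumptions above). No added scan is asked for.

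(c) State the individual decrease criterion as an absolute SUVR change over the actual interval, and give slower build-up its own rate-based definition. Cost: wording only.

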If abnormal results are found from the LP, a neurologist on the study in the Berenson-Allen Center will review the results. The neurologist will determine if the finding is in need of clinical follow-up. If this is the case, the neurologist will speak with the participant, will provide a letter describing the findings and need for follow-up and will be available to speak with the participant's provider if they participant agrees and gives permission to do so.

tACS visits (visits 5-14)

Study visits 5-14 will be conducted in the Berenson-Allen Center for Noninvasive Brain Stimulation at BIDMC. Participants will undergo 10 days (weekdays) of tACS. Participants will be allowed to miss one visit for a total of 9 days of tACS. If they miss more than one visit, additional sessions will be added on if it is within a reasonable timeframe as determined by the investigator, in order to reach a total of 9 sessions. Each session will consist of the following:

- Review of tACS side effects and adverse events will be completed daily before and after stimulation. An assessment of any changes in medication or medical history will be assessed on a daily basis.
- Set up for EEG and tACS which includes cleaning the scalp with alcohol, placing a cap with electrodes on the participant's head and applying gel underneath electrodes
- Three minutes of eyes-closed and eyes-open resting state EEG
- 1 hour of 40Hz tACS stimulation to targeted brain regions
 - Additionally, EEG will be recorded throughout the tACS stimulation
- Cognitive assessment (MoCA) will be completed daily to monitor any cognitive changes. If the score drops by 4 points or more, the covering neurologist will be alerted to assess the participant further. The following day, the patients will repeat a MoCA and if the score has not improved they will be reassessed by the neurologist and the participant will not receive stimulation.
- Subjects will be queried each day about their experience and how they are doing. If participants or their family members express that the participant is having difficulty, study staff will work with them to reduce any burden if possible (e.g. arranging reliable transportation, assuring that they have a snack if needed.....).

Follow Up Visit (Visits 15-18)

The following will occur at the follow up visit within approximately 1 week after the completion of the tACS study visits:

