The CGIC is a way of assessing the AD subject's global change from baseline in a clinical trial. There is a semi-structured baseline interview of the subject and family member or support person. This interview includes questions surrounding the subject's memory, behavior, thought content, and functioning, to name a few. In subsequent visits, the AD subject and family member are interviewed again and the clinician makes an assessment of the subject's change on a Likert-type scale (e.g. improvement, no change, worsening) from baseline.

National Alzheimer's Coordinating Center's Uniform Data Set (NACC-UDS):

The NACC-UDDS is a neuropsychological test battery from the Unified Data Set of the Alzheimer's Disease Centers program of the National Institute of Aging. The battery consists of brief measures of attention, processing speed, executive function, episodic memory and language. The battery includes the following assessments: MoCA, Number Span Forward & Backward, Trail Making Test, Figure Copy, Story Recall, Digit Symbol, and Multilingual Naming Test, Verbal Fluency, Category Fluency.

Cognitive Dementia Rating Scale (CDR):

The CDR is a five point rating scale evaluating the severity of dementia. Six domains are assessed by the clinician using a structured interview of the patient and a family member/caretaker: memory,

orientation, judgment and problem solving, community affairs, home and hobbies, and personal care. These assessments are based upon the subject's cognitive ability to perform in each realm.

Minimental State Exam (MMSE):

The MMSE is a brief, widely used valid and reliable assessment of cognitive impairment. This 30 point questionnaire is used to screen for and estimate severity of cognitive impairment in addition to being used to follow the course of cognitive change over time. The MMSE assesses orientation, attention and calculation, recall, language and repetition and ability to follow complex commands.

Montreal Cognitive Assessment (MoCA):

The MoCA is a widely used 30-point test. It assesses multiple domains including short-term memory recall, visuospatial ability, executive function, attention, concentration, working memory, and orientation. The telephone version of this tool will be utilized for phone follow-up (T-MoCA). The T-MoCA is the same as the eMoCA with the removal of the pencil/paper and visual portions of the assessment. The test takes approximately 10 minutes to complete.

Rey Auditory Verbal Learning Test (RAVLT):

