Undergoing detailed, comprehensive cognitive testing can cause distress in some individuals who may feel they are answering questions incorrectly, stressed by the task demands, tired and fatigued by sustained attentional demands, etc.

Blood Draw

The risks of a blood draw include pain or soreness at the insertion site and bruising.

Genetic Testing

The only potential risk for genetic testing relates to accidental release of protected health information (PHI). All saliva samples will be immediately labeled using only a unique study identifier. The master code for the samples will be maintained in a password-secured file on the BIDMC network drive. Participants will not be informed of the results of the genotyping, nor will that information be entered into their medical history. See **B8. DATA SECURITY** section for more details.

Data Safety Monitoring Plan

Ongoing Cognitive Assessment:

The application of multiple session tACS stimulation has been less frequently studied as compared to tDCS. Prior tACS studies have not reported negative cognitive effects, including a study applying multi-day stimulation in healthy subjects (Polania, Nitsche, Korman, Batsikadze, & Paulus, 2012; Santarnecchi et al., 2016). Additionally, in our current SHARP protocol (IRB # 2017P000011), we and our collaborating sites have run up to 373 healthy subjects through a multi-day tACS protocol without any noted significant problems. Despite this, we will collect a baseline MoCA evaluation. This cognitive testing will be repeated at the end of each stimulation visit. If the score drops 4 points or more from baseline, the covering neurologist will be alerted to assess the participant further, as necessary.

All subjects will be monitored throughout the study for any adverse reactions in relation to the tACS using the Adverse Reaction Form for tACS. Adverse reactions will be reviewed daily prior to tACS and then following tACS. A DSMB will be appointed for this study as described in Part P. Adverse effects will be collected at BIDMC and will be reported to the DSMB every 6 months for review. Serious and unexpected adverse events will be reported to the DSMB simultaneously with reporting to the BIDMC IRB within the designated IRB guidelines. For example, a serious adverse event will be reported by fax or e-mail within 1 business day, followed by a written report within 7 days.

Adverse Event Monitoring

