Adverse effects will be collected from the start of the experimental protocol to the end of study participation. All adverse events, regardless of attribution to tACS or pre/post assessments, will be collected and recorded using standard adverse event forms. Participants will be asked, in an open-ended way, about the presence of any such events. Also, a standard questionnaire for tACS-related adverse effects will be performed in the period after every tACS session. Intensity of each adverse event will be graded as mild, moderate or severe. Events will be medically evaluated as appropriate, including testing and referral.

General Safety Plan

A licensed physician, credentialed at BIDMC will be available by pager during all tACS and TMS visits at

BIDMC. Furthermore, the person applying tACS and TMS will have training in basic life support (BLS) with the availability of emergency equipment. We will monitor patients in detail during and after delivery of tACS, and TMS using an approach drawn directly from suggested guidelines.

Withdrawal Criteria

Subjects may be withdrawn from the trial if:

- A serious adverse event occurs.
- The investigator considers it, for safety reasons, in the best interest of the subject that he/she be withdrawn.

B6. RECRUITMENT AND CONSENT PROCEDURES

Recruitment

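### After a first MoCA drop of 5 or more points, a 1-point gain the next day lifts the stimulation hold while the participant still meets the protocol's own 4-point trigger

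*Combined protocol and SAP*

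**What the plan says.** Three places in the combined protocol and SAP set the rule.

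- **Reference score.** B3.A, Screening and Baseline Visit: "The MoCA will serve as the baseline cognitive assessment for monitoring cognition throughout the study".
- **Trigger.** B3.A, tACS visits: "If the score drops by 4 points or more, the covering neurologist will be alerted to assess the participant further". That sentence names no reference. B5, Data Safety Monitoring Plan (Ongoing Cognitive Assessment) supplies it: "If the score drops 4 points or more from baseline, the covering neurologist will be alerted to assess the participant further, as necessary". B5 also places the daily MoCA at the end of each stimulation visit.
- **Hold.** Only B3.A, tACS visits has one. The MoCA is repeated the following day, and "if the score has not improved they will be reassessed by the neurologist and the participant will not receive stimulation".

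Neither section defines improvement, by size or by a level to be regained. B5 adds no hold of its own.

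**The concern.** The trigger and the hold use different yardsticks. The trigger measures distance from baseline. The hold, as worded, asks only whether the repeat is higher than the score that set off the alert. A participant can therefore pass the second test while still failing the first.

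Safety is Specific Aim 1, and this is the only rule in the protocol that stops stimulation because of a score. Its evident purpose is to stop stimulation when a cognitive fall persists. On a scale of this length ("The MoCA is a widely used 30-point test"), a 1-point gain may be no more than test noise. If the loss is real and persists, the trigger-day and next-day scores differ only by noise, and the repeat will often be the higher of the two.

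**Working it through.** **Step 1: the rule as written.** Let D be the deficit from baseline on the trigger day (D ≥ 4) and g the gain on the repeat. The remaining deficit is D − g. The literal rule holds only if g ≤ 0. The gap is g ≥ 1 together with D − g ≥ 4, which requires D ≥ 5.

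| First drop D | Gain g | Still below baseline by | Literal rule | Still meets trigger? |
|---|---|---|---|---|
| 4 | 1 | 3 | no hold | no |
| 5 | 1 | 4 | no hold | yes |
| 6 | 1 | 5 | no hold | yes |
| 6 | 2 | 4 | no hold | yes |
| 7 | 3 | 4 | no hold | yes |

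Example: baseline 22, trigger score 16 (6 below), repeat 17 (5 below). The repeat has risen, so the hold does not apply. After a first drop of exactly 4, any gain takes the participant out of trigger range and the rule works acceptably.

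**Step 2: the alternative rule.** Hold whenever D − g ≥ 4. If g ≤ 0, then D − g ≥ D ≥ 4, so everyone held by the literal rule is also held by the alternative. The difference between the two hold rates is therefore exactly the gap.

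**Step 3: how often (illustration only).** The documents give no day-to-day SD for the MoCA and no rate of true loss, so both are assumed.

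- SD of a single score: 1 to 2.5 points, with independent normal errors, rounded to whole points.
- True baseline level: spread evenly between 22 and 23.
- True loss L: 0, or 4 to 6 points, the same on the trigger day and the next day.

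With observed baseline B, trigger score T and repeat R, condition on B − T ≥ 4. The literal hold is R ≤ T, the alternative hold is B − R ≥ 4, and the gap is R > T with B − R ≥ 4. Each cell gives literal hold / alternative hold / gap, as a percentage of triggered cases (differences may be off by 0.1 from rounding).

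| SD | L = 0 | L = 4 | L = 5 | L = 6 |
|---|---|---|---|---|
| 1 | 10.6 / 12.6 / 2.0 | 52.0 / 76.0 / 24.0 | 58.8 / 89.4 / 30.6 | 62.2 / 96.7 / 34.5 |
| 1.5 | 17.8 / 25.1 / 7.3 | 45.9 / 73.0 / 27.0 | 51.3 / 83.4 / 32.1 | 55.1 / 91.1 / 36.0 |
| 2 | 21.9 / 33.9 / 12.0 | 42.8 / 71.4 / 28.6 | 47.1 / 79.7 / 32.6 | 50.6 / 86.6 / 36.0 |
| 2.5 | 24.4 / 39.9 / 15.6 | 40.9 / 70.5 / 29.5 | 44.5 / 77.3 / 32.9 | 47.5 / 83.4 / 35.8 |

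First drops of exactly 4 are included in these figures. Dividing the gap by the alternative hold gives the share not held among those whose repeat is still 4 or more below baseline. For SD 2 and L = 5 this is 32.6 / 79.7 = 41%. Over L = 4 to 6 it runs from 32% to 43%.

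**Step 4: timing.** A hold can protect that day's session only if the repeat comes before stimulation. B5 puts the daily MoCA at the end of the visit, and B3.A does not say that the repeat is an exception.

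**The case against.** **The neurologist is involved anyway.** This stands, and it limits the point. The first drop raises an alert. A repeat still 4 or more below baseline is itself a score that raises an alert under both B3.A and B5. Other checks run alongside: "Review of tACS side effects and adverse events will be completed daily before and after stimulation"; a physician on pager during tACS visits; DSMB review; and withdrawal where "The investigator considers it, for safety reasons, in the best interest of the subject that he/she be withdrawn". A reader might infer that a partly recovered participant goes on unobserved. The documents do not support that. What they lack is a mandatory hold, and the reassessment tied to it, before the session. Under B5 the neurologist's response to an alert is left to need.

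**Staff may read improvement as recovery from the drop.** The sentence follows one about a 4-point fall, so this reading is natural. It is not what the text says, however, and two staff members could treat the same score differently. Equally, the protocol does not direct staff to stimulate such a participant; it simply does not stop them.

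**Few cases will arise.** Probably so, with about 10 participants. B5 reports no negative cognitive effects in prior tACS studies and up to 373 subjects in a multi-day protocol without significant problems. Those 373 were healthy subjects, so the reassurance for mild AD is limited. The percentages above are shares of triggered cases. They do not say how many triggers to expect.

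**The revised rule also ends in judgement.** True, since the neurologist may clear the participant. The change is in the default: hold until cleared, instead of proceed unless stopped.

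**Conclusion.** The point holds for first drops of 5 or more. On the literal wording, a gain as small as 1 point removes the hold while the participant is still in trigger range. That conclusion is arithmetic and needs no assumed SD.

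Its frequency does depend on assumptions. With SD 1 to 2.5 and a persistent loss of 4 to 6 points, about 24% to 36% of triggered cases fall in the gap, and the hold rate would rise from about 41%-62% to about 71%-97% under a baseline-referenced rule. With no true loss, the gap is about 2% to 16% of triggered cases, and the hold rate would rise from about 11%-24% to about 13%-40%.

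It would go too far to say that any 1-point gain defeats the rule, because after a drop of exactly 4 it does not. Nor do the documents show that harm is likely, since they give no rate of true cognitive loss under tACS. Endpoints, sample size and analysis are unaffected. This is a cheap improvement to patient safety.

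**What to change.** Replace the hold sentence in B3.A, tACS visits, and refer to it from B5, Ongoing Cognitive Assessment:

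> The MoCA is repeated before stimulation at the next scheduled visit. If it is still 4 or more points below baseline, stimulation is withheld and the neurologist reassesses; stimulation resumes when the score is within 3 points of baseline or the neurologist clears the participant.

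This gives trigger and hold the same yardstick and settles the timing. Tying the repeat to the next scheduled visit also suits a weekday schedule. The clearance route matters because a baseline that was high by chance could otherwise keep a stable participant on hold.

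The cost is the wording plus some extra false holds, each taking a session and a neurologist reassessment. B3.A already makes room for much of this: "Participants will be allowed to miss one visit for a total of 9 days of tACS", and sessions can be added if more are missed.
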